6.6.1 Laboratory Parameters

6.6.1.1 Clinical Safety Laboratory Tests

The clinical safety laboratory tests for patients ≥ 12 kg are presented in [Table 7](#) and will be carried out by the local laboratory of the site (FVIII or FIX concentration as well as inhibitor testing will also be analyzed at the central laboratory) at Screening. Hematology, chemistry, and urinalysis will be repeated as specified in [Appendix 1](#).

Table 7. List of Laboratory Tests

Hematology:	Serum Chemistry:

- Hematocrit (Hct)- Hemoglobin (Hgb)- Platelet count- Red blood cell (RBC) count- White blood cell (WBC) count with differential (automated)- CD4 count¹	
- Albumin (ALB)- Alkaline phosphatase (ALK-P)- Alanine aminotransferase (ALT; SGPT)- Aspartate aminotransferase (AST; SGOT)- Blood urea nitrogen (BUN) or urea- Calcium (Ca)- Chloride (Cl)- Creatinine- Gamma-glutamyl transferase (GGT)- Glucose- Lactate dehydrogenase (LDH)- Potassium (K)- Sodium (Na)- Total bilirubin- Total protein- Troponins
Urinalysis (dipstick): 
- Glucose- Ketones- Microscopic examination of sediment in case of positive dipstick- Nitrite- Occult blood- Protein	
Serology ¹ 
- Hepatitis B surface antigen (HBsAg)- Hepatitis C virus (HCV)- Human immunodeficiency virus (HIV)	Coagulation ¹ : 
- FVIII² or FIX³- FVIII² or FIX³ inhibitors- Prothrombin time (PT)- Activated partial thromboplastin time (aPTT)

Note: laboratory tests may vary depending on the weight of the patient (see [Section 6.6](#)).

¹ At Screening only

² In hemophilia A patients only

³ In hemophilia B patients only

6.6.1.2 Factor and Inhibitor Tests

The concentration of factor VIII (in hemophilia A patients) and FIX (in hemophilia B patients) as well as the titer of inhibitors to FVIII (in hemophilia A patients) or FIX (in hemophilia B patients) will be assessed at Screening. The Bethesda assay will be used for inhibitor testing. FVIII or FIX and titer of inhibitors to FVIII or FIX tests will be performed at the local and central laboratories, except for patients <12 kg where samples will be only collected for testing at the central laboratory.

6.6.1.3 Immunogenicity Testing

Serum samples to test for antibodies against LR769 and any host-related impurities will be taken as specified in [Appendix 1](#). Testing for antibodies against LR769 will be done by a screening assay (electrochemiluminescent method) that is able to detect all antibody isotypes. If the sample is screen positive (which is expected in about 5% of samples), the sample will be tested in a confirmatory assay using binding inhibition as a way to confirm the specificity of the signal seen in the screening assay. If confirmed positive, the sample will be tested in an assay that has been set up to determine if antibodies in patient plasma that are known to bind LR769 (as suggested by the screening and confirmatory assay) will also *neutralize* FVIIa clotting activity. A dot blot assay has been developed to screen the patient samples for reactivity to rabbit's milk proteins. This will allow identification of patients who are generating an immune response to milk proteins as a result of LR769 treatment.

6.6.1.4 Storage Samples

Serum samples will be taken and stored (for a maximum of 5 years after the end of the study) for purposes of any safety evaluations deemed necessary in the future (eg, infectious disease evaluations). These samples will be stored by the Sponsor (or designee) in a central location.

6.6.2 Sample Collection, Storage, and Shipping

A separate laboratory manual will be prepared that will describe the appropriate sample collection, storage, and shipping procedures.

6.7 Dispensing Study Drug

When treatment is taking place in the hospital prior to, during, and after surgery, LR769 will be dispensed to the study staff or patient according to the local procedure of the study center. If the patient has been discharged home, he will be provided with LR769 and directions for its storage, reconstitution and administration.

6.8 Efficacy Assessments

Efficacy Assessments:

The intraoperative efficacy of LR769 will be assessed by the surgeon/practitioner; all other efficacy assessments will be made by the investigator or designee as specified in [Appendix 1](#). Assessments for major and minor procedures will be performed at the same timepoints.

The final assessment (which represents the primary efficacy outcome) will be performed by the investigator at the study center 48 (± 4) hours after the last dose of LR769 and will be based upon the totality of the assessments performed on the patient at each timepoint, also taking into consideration the number of (interventions for) bleeding episodes, oozing, blood transfusions, and the total amount of LR769 used.

All efficacy assessments will be recorded in the patient's source records and on the eCRF.

Intraoperative Assessment of Efficacy by Surgeon/Practitioner

The surgeon/practitioner's rating of intraoperative efficacy of LR769 will be based on the following parameters:

- Estimated blood loss in the surgical patient as compared to the maximum expected volume of blood loss in a patient without a bleeding disorder:
 - Prior to surgery, the surgeon will note if the procedure is major or minor and the type of anesthesia that is planned, and estimate the maximum expected volume of blood loss based upon the type of surgery and the surgeon/practitioner's previous experience in a patient who does not have a bleeding disorder. After the procedure, the surgeon/practitioner will determine the actual characteristics of the procedure and estimate the volume of blood lost during the procedure using the following factors as a guide: volume of drainage fluid, volume of fluid on sponges and towels, fluid replacement given, transfusion requirements, etc. The maximum expected volume of blood loss and the estimated volume of blood loss during the procedure will be recorded.
 - The surgeon/practitioner will assess the intraoperative hemostasis by comparing the estimated intraoperative blood loss with the maximum expected blood loss estimated prior to the procedure as well as the amount of fluid replacement given, transfusion requirements, hemodynamic stability, etc

Comments from the surgeon/practitioner may be necessary if extenuating circumstances occurred (eg, an artery was briefly severed and required additional time for surgical control of the bleeding creating a larger than expected blood loss.

Taking into account the above parameters, the intraoperative response to treatment will be rated as follows:

- Excellent: intraoperative blood loss similar to or less than expected for this type of procedure in a patient who does not have a bleeding disorder and who is undergoing the same surgical or other invasive procedure; no blood component transfusion is required
- Good: intraoperative blood loss that is greater than expected (but not more than 50% greater) for this type of procedure in a patient who does not have a bleeding disorder and who is undergoing the same surgical or other invasive procedure; no unexpected increased blood component transfusion requirement
- Moderate: intraoperative blood loss that is substantially greater than expected (more than 50% greater) for this type of procedure in a patient who does not have a bleeding disorder and who is undergoing the same surgical or other invasive procedure, not explained by a surgical/medical issue other than hemophilia; additional blood component (within 2-fold greater than expected) transfusion is necessary
- Poor: uncontrolled intraoperative blood loss, not explained by a surgical/medical issue other than hemophilia, that requires intervention (rescue therapy requirement [bypass agent or porcine FVIII], and/or increased blood component [>2 -fold greater than expected] transfusion, and/or leads to hypotension or unexpected transfer to Intensive Care Unit [ICU])

Investigator or Designee Assessment of Hemostasis on Postoperative Days

- Excellent: postoperative blood loss similar to or less than expected following this type of procedure in a patient who does not have a bleeding disorder and who is undergoing the same surgical or other invasive procedure; no blood component transfusion is required
- Good: postoperative blood loss greater than expected following this type of procedure in a patient who does not have a bleeding disorder and who is undergoing the same surgical or other invasive procedure, not explained by a surgical/medical issue other than hemophilia; no unexpected need for blood component transfusion
- Moderate: postoperative blood loss that is substantially greater than expected following this type of procedure in a patient who does not have a bleeding disorder and who is undergoing the same surgical or other invasive procedure, not explained by a surgical/medical issue other than hemophilia; additional blood component [within 2-fold greater than expected] transfusion is necessary
- Poor: uncontrolled postoperative blood loss, not explained by a surgical/medical issue other than hemophilia that requires intervention (rescue therapy requirement [bypass agent or porcine FVIII], and/or increased blood component [>2 -fold greater than expected] transfusion, and/or leads to hypotension or unexpected transfer to Intensive Care Unit [ICU])

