6.8.1 Efficacy Endpoints

Primary efficacy endpoint:

- Percentage of surgical or other invasive procedures with a “good” or “excellent” response to LR769 treatment 48 (± 4) hours after the last administration of LR769 as assessed by the investigator

Secondary efficacy endpoints:

- Percentages of success as defined as the combination of “good” and “excellent” responses by the investigator or designee for all efficacy timepoints other than the primary
- Percentages of “poor,” “moderate,” “good,” and “excellent” response by the investigator or designee for all efficacy timepoints
- Percentages of success as defined as the combination of “good” and “excellent” responses by the surgeon/practitioner
- Percentages of “poor,” “moderate,” “good,” and “excellent” response by the surgeon/practitioner for the intraoperative period
- Intraoperative blood loss determined by the surgeon/practitioner as compared to the surgeon/practitioner’s maximum predicted blood loss
- Number of events requiring transfusion between start of procedure and 48 (± 4) hours after last administration of LR769

- Changes in hemoglobin between start of procedure and 48 (\pm 4) hours after last administration of LR769
- Amount of LR769 used. Total, and separated by use in hospital, at home, or for specific reasons (eg, physical therapy, or other reasons like drain or suture removal)
- Number and type of bleeding episodes at the surgical site between start of procedure and 48 (\pm 4) hours after last administration of LR769
- Number of surgical interventions/re-explorations for bleeding episodes between start of procedure and 48 (\pm 4) hours after last administration of LR769

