9.5.1 Primary Efficacy Endpoint

The primary efficacy endpoint is the percentage of surgical or other invasive procedures with a “good” or “excellent” response to LR769 treatment as assessed by the investigator at the study center 48 (± 4) hours after the last administration of LR769; this assessment will be based upon the totality of assessments performed on the patient at each timepoint also taking into consideration the surgeon’s intraoperative hemostatic assessment, the number of (interventions for) bleeding episodes, oozing, blood transfusions, and the amount of LR769 used.

A point estimate of this endpoint will be calculated together with a Clopper-Pearson exact 95% confidence interval.

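### Read literally, the postoperative scale allows substantially greater blood loss without transfusion to be rated Good, and so to count as a primary-endpoint success

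*Protocol*

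**What the plan says.** Protocol 6.8 rates hemostasis on two four-level scales, one intraoperative and one postoperative. The synopsis gives the same definitions. The postoperative scale reads as follows.

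- *Excellent*: loss at or below what is expected, and no transfusion at all.
- "Good: postoperative blood loss greater than expected following this type of procedure"; the excess must have no surgical or medical explanation apart from hemophilia, and there must be "no unexpected need for blood component transfusion".
- "Moderate: postoperative blood loss that is substantially greater than expected following this type of procedure", with the same exclusion of other causes; and "additional blood component [within 2-fold greater than expected] transfusion is necessary".
- *Poor*: uncontrolled loss, with the same exclusion, that calls for rescue therapy or for transfusion more than twofold above expectation, or that results in hypotension or an unplanned ICU transfer.

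The intraoperative scale puts a number on the boundary: "Good: intraoperative blood loss that is greater than expected (but not more than 50% greater". Its *Moderate* begins above 50% and also states that additional transfusion is necessary. Intraoperative *Good* does not carry the clause excluding other causes.

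The primary endpoint (Protocol 6.8.1) is "Percentage of surgical or other invasive procedures with a “good” or “excellent” response to LR769 treatment", as rated by the investigator 48 (±4) hours after the last dose. Protocol 9.5.1 and SAP sections 5 and 7.7.1 say the same. The final rating draws on all assessments, including the surgeon's intraoperative rating, bleeding episodes and interventions for them, oozing, transfusions and the amount of LR769 used. The SAP does not define the categories and adds no threshold or adjudication step.

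**The concern.** The line between *Good* and *Moderate* is the success/failure line of the primary endpoint. On the postoperative scale it has two weaknesses. *Good* has no stated ceiling, and *Moderate* adds a transfusion requirement to the blood-loss requirement. A procedure with substantial excess bleeding and no transfusion can therefore land on the success side.

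Such a case is foreseeable. Protocol 5.2.2 and 5.2.3 allow the dosing interval to be shortened for oozing, and extra LR769 is not among the events that define *Poor*. Surgical re-exploration is a secondary endpoint but is not among those events either. Up to 6 of the minimum 12 procedures may be minor, where transfusion is plausibly rare (an inference; the documents give no rate), so *Moderate* as worded could seldom be reached there.

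The study is single-arm and unblinded, so no control group absorbs a lenient boundary. Nor can the boundary be checked afterwards: the surgeon records a maximum expected loss in advance for the procedure itself (Protocol 6.10), but the documents provide for no advance estimate of postoperative loss.

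**Working it through.** The plan has no figure to reproduce. The sample size rests on adapted guidelines and agreement with authorities (Protocol 9.2, SAP 4), without a null rate, target rate or power. The check is a comparison of wording, followed by an illustration of scale.

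**Step 1: test cases against the written definitions (Protocol 6.8).**

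| Case | Excellent | Good | Moderate | Poor |
|---|---|---|---|---|
| A. Postoperative, hemophilia-related loss substantially above expected; no transfusion, rescue, hypotension or unplanned ICU transfer | No: loss above expected | Yes: both elements met | No: transfusion element absent | No: no qualifying event |
| B. As A, but uncontrolled and needing rescue, or leading to hypotension or unplanned ICU transfer | No | Displaced by the more specific Poor | No: transfusion element absent | Yes, without any transfusion |
| C. Intraoperative loss more than 50% above expected; no transfusion and no event that defines Poor | No | No: over the cap | No: transfusion element absent | No |
| D. Postoperative excess loss explained by a surgical cause | No | No: cause excluded | No: cause excluded | No: cause excluded |
| E. Postoperative loss as expected, with an expected transfusion | No: any transfusion rules it out | No: no excess loss | No | No |

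Case A is the point: the only category that fits is a success. Case C shows that the transfusion requirement in *Moderate* is a fault of both scales. Intraoperatively the case falls into no category; postoperatively it drops into *Good* because the cap is missing. Case D has no category, and nothing in the text shows which way it would be rated. Case E lies between *Excellent* and *Good*, both successes, so it cannot move the primary endpoint.

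**Step 2: scale.** Inputs: at least 12 procedures, at least 6 of them major (Protocol 3.3); Clopper-Pearson exact 95% interval (Protocol 9.5.1). For x successes in n, the lower limit is the 0.025 quantile of Beta(x, n−x+1) and the upper limit is the 0.975 quantile of Beta(x+1, n−x). When x = n the lower limit is 0.025^(1/n) and the upper limit is 100%.

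- One procedure in 12: 1/12 = 8.3 points.
- 12/12 = 100%; lower limit 0.025^(1/12) = 73.5%.
- 11/12 = 91.7% (61.5 to 99.8).
- 10/12 = 83.3% (51.6 to 97.9).
- 9/12 = 75.0% (42.8 to 94.5).
- Major stratum at its minimum: 6/6 = 100%, lower limit 0.025^(1/6) = 54.1%; 5/6 = 83.3% (35.9 to 99.6); 4/6 = 66.7% (22.3 to 95.7).

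The number of affected procedures (0 to 3 of 12 here) is an assumption; the documents give no basis for choosing within it.

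**The case against.** The strongest reply is that the scale is ordinal and should be read as a whole. *Moderate* starts at substantially greater loss, so *Good* must mean greater but not substantially so. The investigator also makes a global judgement and may choose *Moderate* for case A. This stands as far as it goes: a reader might infer that the protocol automatically scores substantial bleeding as success, and it does not. What remains is that the literal definitions support only *Good*, and that the boundary word has no postoperative meaning although the same protocol puts a number on it intraoperatively.

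A reader might also infer that any hemostatic failure managed without transfusion becomes a success. The documents do not support that, because *Poor* covers case B with no transfusion needed.

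Nor are the four definitions the only anchors. The final rating must weigh bleeding episodes and interventions for them, oozing, transfusions, drug use and the intraoperative rating, which carries the 50% threshold.

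The plan also reports all four categories at every timepoint, hemoglobin change, bleeding episodes and re-explorations, with listings of responses, transfusions, interventions and bleeding episodes (SAP 7.7.2). A *Good* rating that sits oddly beside these data would be visible. That helps a reader of the report but does not change what the primary endpoint counts.

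Finally, 8.3 points is what any single reclassification does at n = 12, whatever its cause. This is correct, and the figure is offered for scale only.

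**Conclusion.** The concern holds in a limited form. As worded, substantially greater hemophilia-related postoperative loss, without transfusion, rescue therapy, hypotension or unplanned ICU transfer, fits *Good* and no other category, and may be counted as a primary-endpoint success. The wording permits this rating without compelling it.

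The size is unknown, because the documents do not indicate how often the case will arise. At the minimum of 12 procedures, one such case separates 100% (73.5 to 100) from 91.7% (61.5 to 99.8). Twelve and six are minimums, so the shift per procedure is smaller if more are enrolled. Efficacy is reported descriptively (Protocol 9.5) with no success threshold, so no stated decision would flip; the consequence is for how the estimate is read.

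A reader might also take the uncategorised cases D and E as further evidence of favourable bias. They are not: D has no stated direction, and E is a consistency point between two success categories.

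**What to change.** 1. In Protocol 6.8 and the synopsis, define postoperative *Good* as loss greater, but not substantially greater, than expected. Use the intraoperative 50% figure where a postoperative volume can be estimated.
2. Define *Moderate* as substantially greater loss and/or additional transfusion within twofold, and not meeting *Poor*. Make the same and/or change to intraoperative *Moderate*, which closes case C. The *Poor* proviso stops a rescued case from meeting both categories.
3. Apply the clause on surgical or medical causes consistently across categories, and state how surgically explained excess loss is rated. Removing the clause from *Good* alone would still leave substantial, surgically explained loss without a category.
4. If ratings already exist, add a sensitivity analysis to SAP 7.7.1, beside the one for missing assessments. It would count as non-success any *Good* procedure with a recorded surgical-site bleeding episode that needed intervention or re-exploration. These data are already collected for the secondary endpoints, and SAP 7.1 allows updates before database lock. It would not detect substantial loss that led to no recorded intervention.

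The cost is wording in the protocol and the eCRF guidance, plus one further table if item 4 applies. The success rate may come out slightly less favourable.

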6.8.1 Efficacy Endpoints

Primary efficacy endpoint:

- Percentage of surgical or other invasive procedures with a “good” or “excellent” response to LR769 treatment 48 (± 4) hours after the last administration of LR769 as assessed by the investigator

Secondary efficacy endpoints:

- Percentages of success as defined as the combination of “good” and “excellent” responses by the investigator or designee for all efficacy timepoints other than the primary
- Percentages of “poor,” “moderate,” “good,” and “excellent” response by the investigator or designee for all efficacy timepoints
- Percentages of success as defined as the combination of “good” and “excellent” responses by the surgeon/practitioner
- Percentages of “poor,” “moderate,” “good,” and “excellent” response by the surgeon/practitioner for the intraoperative period
- Intraoperative blood loss determined by the surgeon/practitioner as compared to the surgeon/practitioner’s maximum predicted blood loss
- Number of events requiring transfusion between start of procedure and 48 (± 4) hours after last administration of LR769

- Changes in hemoglobin between start of procedure and 48 (\pm 4) hours after last administration of LR769
- Amount of LR769 used. Total, and separated by use in hospital, at home, or for specific reasons (eg, physical therapy, or other reasons like drain or suture removal)
- Number and type of bleeding episodes at the surgical site between start of procedure and 48 (\pm 4) hours after last administration of LR769
- Number of surgical interventions/re-explorations for bleeding episodes between start of procedure and 48 (\pm 4) hours after last administration of LR769

6.9 Adverse Events Assessments

6.9.1 Performing Adverse Events Assessments

An AE is defined as any undesirable physical, psychological, or behavioral effect experienced by a patient or subject during their participation in an investigational study, in conjunction with the use of a drug or biologic, whether or not product related. Events that match this description but occur between the time of Informed Consent and the first administration of LR769 are also regarded as AEs, but will be listed as *non*-TEAEs. Disease signs, symptoms, and/or laboratory abnormalities already existing prior to Informed Consent are not considered AEs, unless they recur after the patient has recovered from the pre-existing condition or they represent an exacerbation in severity, duration, or frequency.

All AEs will be recorded in the patient's source record and on the eCRFs. A description of the event (preferably medical diagnosis, or if no diagnosis is made, symptom or sign) including start date/time, resolution date/time, seriousness, severity, relationship to LR769, action taken, and outcome will be provided.

All AEs will be followed up until resolution or 30 days after the last dose or early termination, whichever comes first.

